### 9.2.2 Interim Analysis Plan

The study design will include frequent monitoring of the primary outcome with planned looks for both overwhelming efficacy and futility after 33%, 50% and 75% of consecutive enrollments complete 15 day follow-up. For efficacy, we will calculate the posterior probability that the primary outcome event proportion is higher in the saline arm as compared to the CP arm. If this probability is greater than 0.999, then the trial could stop for overwhelming superiority of the CP. This threshold is based on a Haybittle-Peto type boundary, where the stopping threshold is constant across interim looks and the threshold at the final look approximates a design with no interim analyses. For futility, we will calculate a predictive probability (probability of success if the trial were to achieve the predefined maximum sample size). If the probability is less than 0.20 then the trial may stop for futility. Since several factors need to be taken into consideration before stopping a study, a complete report of overall study progress, data quality, and safety will be provided to the DSMB at each interim analysis. If a boundary is crossed, the report will also include secondary outcomes. This information will be taken into consideration by the DSMB in the decision to recommend stopping the study if an efficacy or futility boundary is crossed. The ITT population, defined as all randomized subjects, will be used for the interim analyses.

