### 9.1 Sample Size

Sample size is restricted by the availability of CP for the participating sites. Based on discussions with the NHLBI, we are assured to have sufficient CP available for roughly 300 patients at the time of study initiation.

Therefore, we provide power estimations based on our primary outcome, assuming a maximum of 600 randomizations (300 per group).

Figure 1 provides a range of risk differences (control minus treatment) based on potential event rates for our control population. For example, if the primary outcome event proportion within 15 days from randomization is 20% in the control population, then we have 85% power to detect an absolute decrease of at least 10% in this proportion for those treated with CP. If the control proportion is less than 20% then we can detect differences of roughly 8% while maintaining more than 80% power. Alternatively, if the control rate is closer to 30%, then our power begins to drop for detecting risk differences less than 10%. Based on the current information on hospitalizations in this COVID population, we do not expect the proportion in the standard of care arm to vary greatly from 20%. Clinicians are unlikely to discharge patients whose risk for the primary outcome is significantly greater than 30%..

[figure not shown]

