### 9.2 Analysis Plan

#### 9.2.1 Primary Analysis

Outcomes will be analyzed using the intent-to-treat principle (ITT). The primary analysis for this trial is to test the hypothesis of superiority of CP as compared to saline in the ITT population. To

test this hypothesis, the posterior probability that the proportion of primary outcome events at 15-days post randomization is higher in the saline arm as compared to the CP arm will be calculated. Because little is known about the impact of CP, we assume a non-informative beta distribution for the prior probability. The primary null hypothesis (that the CP proportion is greater than or equal to saline) will be rejected if the posterior probability is greater than or equal to 0.975 (selected to coincide with a one-sided alpha level of 0.025 under a frequentist design). The treatment effect and corresponding credible interval will be constructed.

If the trial fails to enroll the planned sample size due to a significant decrease in the number of COVID-19 patients, then Bayesian posterior and predictive probabilities will be used to assist in the interpretation of the observed data.

Secondary analyses of the primary outcome will explore the impact of potential prognostic variables including age, sex, onset of symptoms duration and site. A logistic regression model will be used for these additional analyses. We will also examine whether participants' pre-treatment antibody levels and/or the genotype of the SARS-CoV2 virus that they carry modify the association between CP and outcome.

The inherent variability in antibody titer among CP units will provide an important opportunity to explore the dose-effect relationship for CP. We envision performing a similar regression of the primary outcome using CP titer categories.

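### At 600 patients, the more-than-80% power stated for an 8-point effect fits a design without the futility looks; section 9.1 should say which rule each power figure uses, at 600 and at 900

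*Combined protocol and SAP*

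**What the plan says.** Section 9.1 gives two power statements, both for 600 randomised patients (300 per arm). At a 20% control rate, "then we have 85% power to detect an absolute decrease of at least 10" per cent. Below that rate: "If the control proportion is less than 20% then we can detect differences of roughly 8% while maintaining more than 80% power". It adds that "we do not expect the proportion in the standard of care arm to vary greatly from 20" per cent.

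Section 9.2.1 sets the final criterion. The null hypothesis is "rejected if the posterior probability is greater than or equal to 0.975 (selected to coincide with a one-sided alpha level of 0.025" in frequentist terms), and "we assume a non-informative beta distribution for the prior probability".

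Section 9.2.2 provides "planned looks for both overwhelming efficacy and futility after 33%, 50% and 75% of consecutive enrollments complete 15 day follow-up". The efficacy threshold is a posterior probability above 0.999. For futility the quantity is the predictive probability of success at the maximum sample size: "If the probability is less than 0.20 then the trial may stop for futility". The DSMB weighs study progress, data quality and safety before recommending a stop. Section 9.2.2 explains the choice of the efficacy boundary only.

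The readable text does not say how often the futility rule would stop a trial of an effective plasma, or whether the power figures allow for it. Figure 1, the power display, is not available in the text reviewed. Sections 1.1, 1.2 and 5.4 now give a maximum of 900, while the power text in 9.1 is still written for 600.

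**The concern.** A futility rule lowers power, because some trials that would have succeeded are stopped early. A predictive-probability cut of 0.20 applied three times, first at one third of the information, is not negligible. If printed power ignores the rule, the sponsor and DSMB hold a figure for a different design from the one being run. They also lack the number they need when the boundary is crossed: how often that happens when plasma works as well as the plan hopes.

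**Working it through.** **Inputs.** From the protocol: 1:1 allocation (6.3); 300 per arm behind the power text (9.1) and 450 per arm in force (1.2); final success at posterior ≥ 0.975 (9.2.1); efficacy stop above 0.999 and futility stop below 0.20, with looks at 33%, 50% and 75% (9.2.2). Assumptions: a Beta(1,1) prior, since the parameters are not given; complete data; the futility boundary followed at every look; looks at 100/150/225 per arm of 300 and 150/225/338 per arm of 450.

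**Step 1. Reproduce the printed figures without futility.** With d = pC − pT and p̄ the mean of the two rates,

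power = Φ{ [d − 1.96·√(2p̄(1−p̄)/n)] / √(pC(1−pC)/n + pT(1−pT)/n) }.

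- 18% vs 10%, n = 300: √(2×0.14×0.86/300) = 0.02833 and √((0.1476+0.09)/300) = 0.02814. Then (0.08 − 0.05553)/0.02814 = 0.870, giving 80.8%.
- 20% vs 10%, n = 300: (0.10 − 0.05714)/0.02887 = 1.485, giving 93.1%.

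The formula gives 88.1% at 15% vs 7%, 85.6% at 16% vs 8% and 78.5% at 19% vs 11%. The 8-point claim therefore reproduces for control rates up to about 18% and is within 2 points at 19%. The 85% for 20% vs 10% does not reproduce this way. It is 91.5% with a continuity correction and 90.4% with 10% missing, so the printed figure is below all of these.

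**Step 2. Apply the futility rule.** At a look with n per arm and xC, xT events, the predictive probability is the sum over future counts yC, yT of

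BB(yC; N−n, 1+xC, 1+n−xC) × BB(yT; N−n, 1+xT, 1+n−xT) × 1{P(pC > pT | xC+yC, xT+yT) ≥ 0.975},

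where BB is the beta-binomial probability. For example, at 100 per arm with 20 control events, 18 plasma events is the smallest count that triggers futility (predictive probability 0.167). Under 20% vs 10%, 10 would be expected. Power and stopping rates then come from an exact binomial forward recursion over the looks.

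**Step 3. Results at 600.**

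| Control vs CP | Power, no futility stop | Power, rule followed | Futility stop | Net loss (points) |
|---|---|---|---|---|
| 15% vs 7% | 88.8% | 81.8% | 14.0% | 7.0 |
| 16% vs 8% | 86.2% | 78.5% | 16.4% | 7.7 |
| 18% vs 10% | 81.2% | 72.9% | 20.5% | 8.3 |
| 19% vs 11% | 78.9% | 70.4% | 22.2% | 8.5 |
| 20% vs 10% | 93.5% | 87.5% | 9.9% | 6.0 |

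The second column keeps the efficacy looks. Removing them as well changes power by no more than 0.3 points (81.1% at 18% vs 10%), so the loss comes from the futility rule. A Beta(0.5,0.5) prior moves each figure by less than 1 point. With 10% lost (270 per arm), power with the rule is 84.0% at 20% vs 10% and 68.3% at 18% vs 10%.

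**Step 4. Results at 900, rule followed.**

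| Control vs CP | Power | Futility stop |
|---|---|---|
| 20% vs 10% | 96.5% | 3.0% |
| 18% vs 10% | 88.2% | 9.2% |
| 19% vs 11% | 86.4% | 10.6% |
| 30% vs 20% | 87.7% | 9.7% |
| 30% vs 22% | 70.0% | 22.5% |

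Without futility stopping, the last four rows would be 93.7%, 92.3%, 93.5% and 78.2%.

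**The case against.** The strongest reply is that 600 is no longer the maximum. At 900 the 8-point claim holds with the rule followed at every control rate checked from 10% to 21%. Even if the first look used the 600 maximum and later looks used 900, power is 92.3% at 20% vs 10%, 82.3% at 18% vs 10% and 80.4% at 19% vs 11%. This stands, and it limits the point to what 9.1 says. It does not remove the point, because 9.1 still prints the 600-patient claim and gives no figure for 900. Section 9.1 ties an increase to an overall event rate above the assumed one. At 30% vs 22%, 900 patients give 70.0%. The plan makes no 80% claim there, however, and warns that power falls near a 30% control rate for differences under 10 points.

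A second reply is that the rule is permissive and the DSMB uses judgement. That also stands: the figures assume the boundary is followed, and actual power lies between the two power columns. A third is that 9.1 says roughly 8 points. At 9 points the rule still gives 83.5% (18% vs 9%) and 81.3% (19% vs 10%) at 600.

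A reader might infer more than the documents support:

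- *That all the power text ignores futility.* The printed 85% is below the no-futility 93.5% and close to the with-rule 87.5%, so it may already include the rule.
- *That the stop rate is the power lost.* Some stopped trials would have failed anyway. The net loss at 600 is 6 to 8.5 points in the scenarios tabulated.
- *That the 0.20 cut is an error.* A cut of 0.05 would give 79.4% at 18% vs 10% at 600. It would also raise expected enrolment under no effect from about 270 to 340 of 600, or from about 405 to 510 of 900. That is a trade-off for the sponsor and DSMB.

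**Conclusion.** The point holds as a reporting defect in 9.1 and 9.2.2. At 600 patients, more than 80% power for 8 points describes a design without futility stopping. With the rule followed, it holds only for control rates up to about 15%, and power falls to 70.4% at 19% vs 11%. The 85% statement is met either way, so the two power statements in 9.1 appear to rest on different rules and the readable text does not say which. The documents do not support calling the trial underpowered for 8 points at the current maximum when the control rate is below 20%.

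The result rests on a flat beta prior, complete data and the non-binding boundary being followed. Figure 1 could not be checked and may carry information that the text lacks.

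**What to change.** 1. In 9.1, restate power with the futility looks included, for 600 and for the 900 in force, and say for each figure whether futility stopping is included. At 600, either limit the more-than-80% claim for 8 points to control rates of about 15% or less, or state that this 8-point figure excludes futility stopping. Do not attach that statement to the 85% figure unless its derivation confirms it.
2. In 9.2.2 and the DSMB interim report, give the futility-stop probability under 8- and 10-point effects at 900. On the assumptions above this is 9.2% at 18% vs 10%, 10.6% at 19% vs 11% and 3.0% at 20% vs 10%. Add 30% vs 20% (9.7%) and 30% vs 22% (22.5%) for higher control rates. Note that these assume the non-binding boundary is followed.

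No change to the 0.20 cut is recommended. The cost is a wording amendment and a less favourable printed power figure at 600, with no additional patients and no change to the decision rules.

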### 9.2.3 Missing Data

Although every attempt will be made to prevent incomplete data, a certain amount of missing data is inevitable due to losses to follow-up or withdrawn consents. For the primary outcome data, subjects who do not complete the follow up because of withdrawal of consent will be considered missing. In the case of loss to follow-up, we would expect that the sites will be able to obtain information on the event within 15 days from randomization from the medical record; if the site cannot obtain information, the outcome will be considered missing. At the time of the planned analyses, the unblinded statistician will conduct a thorough analysis of outcome variables, reasons, and patterns of missing data, and provide this information in the DSMB report. Sensitivity to missing data will be assessed. If the outcome is insensitive to missing data, defined as no change in the conclusion regardless of the set of imputed values, each missing observation will be imputed an unfavorable outcome (i.e., event occurred). If the

outcome is sensitive to missing data, each observation will be imputed using a Bayesian imputation model.

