##### Completed

Subjects are considered completed when they are followed through Study Day 30 and complete the final study follow-up visit scheduled for that time.

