### **6.4 Concomitant Therapy and Hospitalization**

Concomitant medications will be documented on the CRF. We will not enroll patients already in another clinical trial. Subjects should not enroll in another interventional trial as an outpatient while in this clinical trial.

In the event that a subject worsens and is admitted to a hospital, that subject will have met the primary endpoint of this trial. We will not restrict that subject from enrolling in another trial if eligible, especially because other trials may be the only access for potential COVID-19 therapies. In particular, control subjects should be eligible for compassionate use CP, though this trial cannot guarantee CP will be available at a site precisely when the subject is hospitalized. Patients in either arm who develop severe/critical disease are not precluded from receiving compassionate use CP after meeting the primary endpoint, if this therapy is available for routine clinical care at the institution where they receive care.

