#### 8.1.1 Primary Endpoint

These events can be ascertained from the subject or informant report during follow-up calls, electronic health record review, death notices, or direct contact with the subject during follow-up visits. Thus, we have multiple opportunities to collect and confirm the primary endpoint, minimizing risk of missing data.

Subjects will meet the primary endpoint of the study (1) if they are admitted to a hospital as an inpatient/observation status for any reason during the 15 days following randomization, (2) if they have an emergency department or urgent clinic visit during the 15 days following randomization, or (3) die outside the hospital during the 15 days following randomization. Scheduled medical follow-up visits or rechecks will not meet the definition of emergency care.

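### Section 9.2.3, read literally, sets the primary outcome to missing on withdrawal of consent even when a qualifying event is already recorded; this conflicts with sections 6.4 and 8.1.1 and can matter when the result is close

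*Combined protocol and SAP*

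**What the plan says.** Section 9.2.3 treats two routes to incomplete follow-up differently.

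- Withdrawal of consent: "For the primary outcome data, subjects who do not complete the follow up because of withdrawal of consent will be considered missing". The only condition is that follow-up was not completed because consent was withdrawn.
- Loss to follow-up: the site first looks for the outcome in the medical record, and only "if the site cannot obtain information, the outcome will be considered missing".

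Missing outcomes are then imputed in one of two ways. When no set of imputed values changes the conclusion, the rule reads: "each missing observation will be imputed an unfavorable outcome (i.e., event occurred". In the other branch, a Bayesian model supplies the values instead.

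Elsewhere the endpoint is met when the event happens. Section 6.4 says of a participant who is admitted that "that subject will have met the primary endpoint of this trial". Section 8.1.1 counts participants "if they are admitted to a hospital as an inpatient/observation status for any reason during the 15 days following randomization", and likewise for emergency or urgent visits and for death outside the hospital in the same window. Section 9.2.1 specifies an intention-to-treat primary analysis, and section 9.2.2 defines that population as everyone randomized.

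Section 9.2.3 does not define the follow-up it refers to. Section 9.2.2 times the interim looks "after 33%, 50% and 75% of consecutive enrollments complete 15 day follow-up". Section 4.3 says "Subjects are considered completed when they are followed through Study Day 30", and it counts withdrawal at any time between dosing and the end of Day 30 as discontinuation.

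**The concern.** Take a participant admitted on Day 4 who withdraws consent on Day 10. Under 6.4 and 8.1.1 this person has met the primary endpoint, and later withdrawal cannot undo that. Under the wording of 9.2.3 the same person has a missing outcome. This holds whether follow-up means 15 or 30 days.

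Withdrawal after an admission or emergency visit may well be related to outcome. It could also differ by arm, since section 1.5 lets a hospitalized participant ask for the allocation. The overwritten values would then not be a random subset. Reclassifying known events as missing also enlarges the set of values that can be varied in the sensitivity check, which makes the model-based branch more likely to apply. At stake is whether the primary posterior probability rests on imputed values where observed ones exist.

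The point concerns which outcomes are classed as missing, not the choice of imputation method.

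**Working it through.** The plan gives no figure for withdrawals, so there is none to reproduce. The conflict is one of wording; the arithmetic only shows when it could matter.

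**1. Where the rule can do harm.** In the insensitive branch every missing value is imputed as an event. A recorded event set to missing returns as an event, and the conclusion is fixed by definition. A known event can be lost only in the sensitive branch.

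**2. Inputs.**
- 450 per arm: revised maximum, sections 1.1 and 1.2.
- Success if the posterior probability is at least 0.975: section 9.2.1.
- Prior: 9.2.1 says only non-informative beta. Beta(1,1) is assumed, with Beta(0.5,0.5) as a check.
- Event counts of 90 saline and 66 plasma: assumed, chosen near the boundary (20.0% and 14.7%).
- Withdrawals after a recorded event, 4 saline and 1 plasma: assumed.

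**3. Formula.** With x events of 450 in an arm, that arm's event proportion has posterior Beta(1 + x, 1 + 450 − x). The quantity of interest is Pr(p_saline > p_CP), by numerical integration.

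**4. Recorded events kept.** 90 vs 66 gives 0.983, which is success.

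**5. Recorded events set to missing.** The observed data become 86 of 446 and 65 of 449.
- Branch check: the least favourable fill-in for plasma (4 saline non-events, 1 plasma event) is 86 vs 66, giving 0.962. The most favourable is 90 vs 65, giving 0.986. The conclusion changes, so the sensitive branch applies.
- Imputing at the remaining arm rates: saline 86/446 = 0.193, so 86 + 4 × 0.193 = 86.8 expected events; plasma 65/449 = 0.145, so 65 + 0.145 = 65.1.
- Result: 0.973, which is not success. Beta(0.5,0.5) gives the same pair, 0.983 and 0.973.

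Five of 900 participants (0.6%) are enough in this example.

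**6. How narrow the window is** (same method, Beta(1,1)).

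| Events, saline vs CP | Withdrawals after an event, saline / CP | Events kept | Set to missing, arm-rate imputation |
|---|---|---|---|
| 90 vs 66 | 4 / 1 | 0.983 | 0.973 |
| 90 vs 66 | 2 / 1 | 0.983 | 0.980 |
| 90 vs 66 | 4 / 4 | 0.983 | 0.985 |
| 90 vs 65 | 4 / 1 | 0.986 | 0.978 |

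Only the first row crosses 0.975. The shift can go either way, depending on which arm loses proportionately more events.

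**7. The undefined follow-up.** If it means 15 days, someone who withdraws on Day 20 has completed it and keeps the outcome. If it means Day 30, an event-free result already established at Day 15 would be set to missing. As a conditional illustration, take 90 vs 45 events of 450 (20% vs 10%), and suppose 9 saline and 18 plasma participants withdraw event-free between Day 16 and Day 30.
- Least favourable fill-in: 90 vs 63, giving 0.992. The conclusion cannot change, so all 27 are imputed as events.
- Rates become 99/450 = 22.0% and 63/450 = 14.0%. The difference falls from 10.0 to 8.0 points, while superiority is still declared (0.999).

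This needs both the Day-30 reading and a two-to-one imbalance in withdrawals, which nothing in the documents supports.

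**The case against.** The strongest reply is that 9.2.3 opens by discussing incomplete data, and a recorded event is not incomplete. With 6.4, 8.1.1 and intention to treat, the sentence can be read as covering only outcomes still unknown at withdrawal. That may well be the intent, but the wording does not say it, and the next sentence shows that the authors could condition missingness on whether the outcome was known. The different treatment of loss to follow-up is not in itself a fault, since a participant who has withdrawn may not permit a record search. Keeping an event already recorded needs no such search.

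The reply is right on size. Section 7.2 aims for more than 90% follow-up, and section 10.2 reports very low withdrawal in the network's earlier trials. At the planning rates the rule loses no recorded events. With 90 vs 45 events of 450, suppose 8 saline and 2 plasma participants withdraw after an event. The least favourable fill-in is 82 vs 45, giving 0.9998, so the insensitive branch applies and all 10 return as events.

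A reader might infer two stronger points that the documents do not support. One is that the rule dilutes the effect generally; recorded events can be lost only when the result is close enough to be sensitive. The other is that Day-15 event-free outcomes are discarded. That needs the Day-30 reading, and the 15-day wording in 9.2.2 and within 9.2.3 itself makes the 15-day reading at least as natural.

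**Conclusion.** The concern holds in a limited form. As written, 9.2.3 classes recorded primary events as missing after withdrawal of consent, contrary to 6.4 and 8.1.1 and inconsistent with intention to treat. That conclusion rests on the text and on no assumed number.

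The practical effect is confined to close results. In a constructed case near the boundary, five withdrawals after an event move the posterior probability from 0.983 to 0.973 and reverse the decision; modest changes to that case leave the decision intact. The example rests on assumed event counts, assumed and unbalanced withdrawals, a Beta(1,1) prior and arm-rate imputation. The real size cannot be estimated without a withdrawal rate, and it is small if withdrawals are few and balanced.

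The meaning of follow-up in 9.2.3 is a separate ambiguity to be closed. It is not an established loss of data.

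**What to change.** Replace the sentence on withdrawal of consent in 9.2.3 with text to this effect:

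- Follow-up for the primary outcome is the 15 days after randomization.
- Data collected up to withdrawal of consent are retained.
- A participant with a qualifying event recorded on or before the date of withdrawal is analyzed as an event.
- A participant known to be event-free through Day 15 is analyzed as a non-event, whatever happens later.
- Only a participant who withdraws before completing Day 15 without a recorded event has a missing primary outcome.

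The cost is a short rewording of one section, with no new data and no added visits. It should be agreed before the final analysis by people without access to outcomes by arm, because a choice made later could look driven by the result.
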